### **I. Project Summary and Project Goals**

Sexual assault of college women is a serious and complex public health problem: one in five college women report being sexually assaulted. The purpose of this study is to conduct a randomized controlled trial study with 750 female college students from three universities to test the efficacy of RealConsent-F, a sexual violence risk reduction program for college women, compared to an attention-placebo comparison condition. The primary outcome will be self-reported sexual violence victimization and the secondary outcomes will be alcohol and dating protective- and risk-related behaviors and resistance strategies. Our expected outcomes are demonstrated feasibility and efficacy of a technologically novel risk reduction program for female college students.

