## Baseline Assessment, Randomization, and Completion of RealConsent or Stress

### Management:

Once a participant is registered, she will get a confirmation email; her response will trigger another email that contains a link to the online baseline survey and a password for accessing. To enhance confidentiality of responses, we will encourage participants to choose a private location, use a secure, encrypted Internet connection, and close their web-browser after they have completed a survey. Once an individual completes the baseline survey, she will be randomized using an automated stratified block randomization program to either RealConsent-F or to Stress Management programs. Stratified block randomization will ensure equal numbers between conditions and that 125 participants from each university are assigned to each condition.

We will communicate to the research participants and encourage them to complete their assigned task (RealConsent-F or Stress Management) within two weeks. Participants can complete the modules at their own pace within the 2-week window and are able to leave a module and finish it later. Email prompts will be sent every 48 hours to remind participants to complete the modules. Participants will be contacted by email and/or text message prior to 6 months post-intervention (Spring 2019) to complete the posttest.

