### Study Measures

The table below displays the measures that will be used in all study assessments.

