### Statistical Analysis

The complex empirical methods described below will be conducted by [name], an experienced statistician and colleague of [name]. Data analysis will be performed using the SAS Software System. Descriptive statistics for all measurements will be estimated and reported. Frequency distributions will be created to screen for any errors and will be used to summarize categorical data; measures of central tendency and dispersion will be used to summarize continuous data. All data will be examined for bivariate relationships and results used to build a multivariate statistical model.

We will analyze our study data with an intent-to-treat and per protocol analyses. An intent-to-treat analysis includes all participants who were randomized, regardless of compliance, withdrawal, and anything that happens after randomization. An advantage is that it is an analysis based on original randomization; however, effect estimation may be conservative and misleading with increasing attrition. A per protocol analysis considers only participants who fully complied and completed the study. Per protocol is less conservative and may reflect true treatment differences for those with full compliance. Including an intent-to-treat and per protocol analysis will provide a more complete understanding of treatment effects. Because we will most likely encounter incomplete data due to dropouts and non-response, multiple imputation of missing data will be used to impute missing values based on other available covariates.

Outcomes, including victimization and frequency of risky dating behaviors and alcohol-protective behaviors will be modeled using a general linear mixed model. This is an appropriate statistical model to use with repeated measures data collected over time. A random effect for subject will be included to account for the multiple measurements taken at baseline and 6-month follow-up on each subject. Treatment group and demographics will be included as fixed effects in the model. Mediation models will be tested with a two-tiered approach for mediation testing, with bootstrapping to generate estimates of the indirect effect and 95% confidence intervals.

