### Sample Size

Primary outcome will be report of victimization; secondary outcomes are protective- and risk- related behaviors. Sample size is based on the number per group needed to detect clinically meaningful treatment effects on victimization. Calculations were based on 80% power, level of significance of .05, and two- tailed statistical tests. Clinically meaningful treatment efficacy was defined for our outcome variable as having between a small and moderate effect size (Cohen's  $h \geq .35$ ). This effect size was considered as a 9% point difference between groups, at a minimum, and could potentially translate to a clinically significant reduction in the number of victimizations on those college campuses that implement RealConsent. Based on previous research with female college students, assuming incidence of 0.22 without intervention and .13 with intervention, a total of 558 participants are needed (279 in each group). We expect 20% attrition based on previous work. To achieve adequate power, we estimate a needed sample size of at least 670; however, we are increasing sample size to 750 participants (375 in each group) to increase power.

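### The trial is sized as a comparison of two proportions, but the planned two-wave linear mixed model and the undefined primary variable are not shown to be the analysis that was powered

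*Combined protocol and SAP*

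**What the plan says.** Section I names the endpoint without a scoring rule or a time window: "The primary outcome will be self-reported sexual violence victimization". The Sample Size section repeats it ("Primary outcome will be report of victimization") and sizes the trial "assuming incidence of 0.22 without intervention and .13 with intervention", with no period attached to either rate. It adds "This effect size was considered as a 9% point difference between groups, at a minimum" and "Calculations were based on 80% power, level of significance of .05, and two- tailed statistical tests". The result is 558 women, 279 per group. With 20% attrition expected, 750 (375 per group) are planned.

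Table 1 gives the primary measure as the Revised SES, with 35 items and an alpha of .74. It is introduced by "The table below displays the measures that will be used in all study assessments".

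The Statistical Analysis section states: "Outcomes, including victimization and frequency of risky dating behaviors and alcohol-protective behaviors will be modeled using a general linear mixed model". It gives the model a random subject effect to cover the baseline and 6-month measurements. The only fixed effects it lists are treatment group and demographics. It mentions neither a time term nor a treatment-by-time term, and it does not say which contrast is the primary test.

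On timing, the section on baseline assessment, randomization and program completion says that women are contacted "prior to 6 months post-intervention (Spring 2019) to complete the posttest", after a self-paced program window of two weeks.

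**The concern.** The sizing is for a binary outcome compared once, after treatment. The analysis is a model for continuous outcomes in which the baseline value is part of the response. Three things needed to connect them are missing: the rule that turns SES answers into the endpoint, the period that the follow-up answer covers, and the contrast that tests efficacy.

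Two consequences follow. First, a treatment term with no treatment-by-time term estimates the group difference averaged over baseline and follow-up. Randomization makes the expected baseline difference zero, so the averaged effect is half the follow-up effect. Second, if the follow-up question reaches back before randomization, it counts events that the program could not have prevented. These add similarly to both arms and shrink the contrast. Leaving the scoring, window and contrast open also allows them to be settled after the data are seen.

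**Working it through.** **Inputs.** From Sample Size: rates .22 and .13, two-sided alpha .05, power 80%, 375 per group, 20% attrition. Observed per arm: 375 × .80 = 300. Assumed, because the documents do not give them: the baseline–follow-up correlation r (0 to .6), the baseline rate, and the recall period.

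**1. The plan's own figure.** With the pooled-variance formula and mean rate .175:

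n = [1.96·√(2 × .175 × .825) + .8416·√(.22 × .78 + .13 × .87)]² / .09² = (1.0532 + .4491)² / .0081 = 278.6, so 279 per group and 558 in total.

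The stated figure is reproduced. The same test has power .83 with 300 per arm and .90 with 375.

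**2. A linear model on the 0/1 follow-up value alone.** SE = √[(.22 × .78 + .13 × .87)/300] = .0308; .09/.0308 = 2.92; power .83. Using a linear model for a binary outcome is therefore not in itself what costs power.

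**3. The model as listed.** With both waves observed and a random subject effect, the treatment coefficient is the group difference in each woman's two-wave mean. Expected effect: (0 + .09)/2 = .045. With equal variance V = .175 × .825 = .1444 at both waves, the variance of the two-wave mean is V(1 + r)/2, and SE = √(2 × variance/300).

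- r = 0: SE .0219, ratio 2.05, power .54
- r = .2: SE .0240, ratio 1.87, power .47
- r = .4: SE .0260, ratio 1.73, power .41
- r = .6: SE .0277, ratio 1.62, power .37

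If instead the baseline rate is .22 in both arms, baseline variance is .1716 and the average follow-up variance is (.1716 + .1131)/2 = .1424. The variance of the mean is then (.1716 + .1424 + 2r√(.1716 × .1424))/4, and power is .50 at r = 0 and .34 at r = .6. Over both variance assumptions the range is about .54 to .34.

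**4. Other contrasts on the same data** (equal variance, r = 0 / .2 / .4 / .6):

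- Treatment-by-time (change), variance 2V(1 − r): .54 / .63 / .75 / .90
- Follow-up value adjusted for baseline, variance V(1 − r²): .83 / .84 / .89 / .95

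The unstated choice of contrast therefore matters a great deal. Of these options, only baseline adjustment keeps the planned power at every r.

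**5. Recall that reaches before randomization.** Suppose .22 and .13 are the risks over the 6 months of follow-up, and the pre-randomization risk runs at the control rate.

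- 9 months in total: pre-randomization risk 1 − .78^(3/6) = .117. Rates are 1 − .78 × .883 = .311 and 1 − .87 × .883 = .232; difference .079; power .59 with 300 per arm.
- 12 months in total: pre-randomization risk .22. Rates are 1 − .78² = .392 and 1 − .87 × .78 = .321; difference .070; power .43.
- 12 months at half the control hazard: pre-randomization risk 1 − .78^½ = .117, the same rates as the 9-month case; power .59.

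**The case against.** The sponsor can fairly say that the endpoint is evidently yes/no. The Sample Size section speaks of report and incidence, and uses an effect size for proportions. A 0/1 follow-up value in a linear model loses almost no power (step 2). A competent analyst might add the interaction or adjust for baseline without being told. The follow-up question may already be limited to 6 months or to the time since the last survey. Using the same instruments does not prove an identical time stem, and the questionnaire is not reproduced.

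Much of this stands, and it rules out several stronger readings.

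- *That the plan analyses a 35-item total score.* Table 1 gives item counts for every measure, and alphas where available. No text says that an SES total is the endpoint.
- *That a score would necessarily have much less power.* In a simulated comparison of mean counts at follow-up, with 300 per arm, victims averaged 2, 4 or 6 events (1 plus a negative binomial count, dispersion 1, 1 and .5). Power was about .64, .56 and .42 when victims average the same number in both arms. It was about .87, .91 and .78 when treated victims average 1.7, 3 or 4.5. The documents support neither assumption over the other.
- *That .22 and .13 are 6-month rates.* No period is given. Six months is inferred from the schedule.
- *That follow-up runs from each woman's program completion.* The text also gives a calendar anchor, Spring 2019. The shift is about two weeks if the window is kept, and different timing by arm is speculation.

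What the objection does not answer is that a yes/no reading still leaves the listed model without the term that isolates the follow-up effect, and that no text bounds the follow-up answer.

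**Conclusion.** The point holds as a mismatch combined with missing definitions. The documents do not prove that the outcome analysed differs from the outcome powered; they fail to show that it is the same. As written, the model does not deliver the stated 80% power: about .54 to .34 for a 0/1 outcome with 300 per arm, against .83 for the test used in sizing. That range depends on reading the fixed-effects list literally and on assumed correlations of 0 to .6. The recall figures of .59 to .43 are conditional on an assumed 9- to 12-month window, with pre-randomization risk at the control rate. They show what an unbounded question could cost, not that contamination will occur. The timing anchor is minor. Because the primary conclusion rests on this definition and the repair is cheap, it should be made before follow-up starts; recall that was not bounded at collection cannot be bounded afterwards.

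**What to change.** 1. In Section I, Table 1, Statistical Analysis and Sample Size, state one primary endpoint: at least one SES-positive experience (yes/no) since randomization, or since the baseline survey. State the period to which .22 and .13 refer.
2. Bound the follow-up SES stem to that date.
3. Name the primary test: treatment effect on the follow-up value in a binary model (logistic or risk difference), adjusted for baseline SES history and for university, by which the allocation is balanced. Make any SES frequency or severity score secondary.
4. Set the 6-month survey date from randomization for every woman, so that those who do not finish the modules, whom intent-to-treat retains, also have a defined date.

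The cost is protocol and SAP wording, one survey stem and one reminder date. The two-proportion sizing of 279 per group then applies to the endpoint analysed, and the planned 750 needs no increase on this account.

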## **VI. Quality Assurance**

### Data Safety & Monitoring Plan

In accordance with the NIH recommendations as this is a NIH clinical trial we will have a Data Safety Monitoring Board (DSMB). The proposed study is considered to present minimal risk to participants, given that they will complete surveys and possibly participate in a sexual violence prevention educational program. Members of the DSMB will perform the following activities:

1. Review the research protocol and plans for data and safety monitoring.
2. Review progress of the trial, including analysis of data quality and timeliness; subject recruitment and retention; subject risk versus benefit; and other factors that may affect outcome.
3. Review serious adverse event reports, provide commentary, and provide oversight to ensure that reports are relayed to individual IRBs and to the Office of Human Research Protections (OHRP), as indicated.
4. Review analyses of outcome data and review reports of related studies to

- determine whether the current study needs to be changed or terminated.
5. Determine whether the trial should continue as designed, should be changed, or should be terminated based on the data and make recommendations to the NIH and the Institutional Review Board considering conclusion or continuation of the study.
  6. Review proposed modifications to the study prior to their implementation.
  7. Protect the confidentiality of the trial data and the results of the monitoring.
  8. Determine whether and to whom outcome results should be released prior to the reporting of study results.
  9. Following DSMB meetings, provide appropriate NIH staff with written information concerning their findings.

The DSMB members will be chosen by [name] and will be reviewed and approved by the NIH Project Officer. The members, who will all be voting members, will be chosen based upon their knowledge of clinical trial methodology, their experience with the topical area (i.e., sexual violence risk reduction strategies), and absence of conflicts of interest. They will be appointed for the life of the project. The Chair of the DSMB will be selected from among the DSMB members. The NIH Project Officer will serve as an ex-officio member of the DSMB.

DSMB meetings will be held every 12 months beginning in Year 1 of the study. Serious adverse events will be reported to the Chair as soon as they occur. The Chair of the DSMB will determine whether an in-person meeting or teleconference is needed. Prior to the meetings, a written report containing any study preliminary findings will be sent to DSMB members. Preliminary findings will not be made available to individuals outside of the DSMB. Each meeting will include time to review the progress of the study and to answer questions from members of the DSMB. Members of the DSMB will disclose any potential conflicts of interest, either pre-existing or those that develop during their tenure, to the Principal Investigator and the NIH Project Officer.

In accordance with NIH policy, a data and safety monitoring plan has been developed for the proposed study. [name] will provide oversight of all recruitment and study procedures and quality assurance checks will be conducted as planned. All records pertaining to the study and all of the original and electronic files containing collected data will be securely stored. [name] will be solely responsible for dissemination of study findings through presentation and publication formats. Presentations and publications will not disclose the name of the clinics where recruitment occurred. [name] will also be solely responsible for handling any requests from other investigators to examine the data collected during Phase II of this Fast-track proposal. [name] will present these requests to a Data and Safety Monitoring Board (DSMB) for their consideration.

This research team has extensive experience working with college student populations and extensive experience confronting ethical issues of subjects in behavioral

interventions. We will work with all respective IRBs involved to assure compliance with ethical and HIPPA standards. Additionally, no incentives (i.e., “finder’s fees) will be provided to staff for recruiting or referring subjects into the study. Moreover, we are going to make it abundantly clear to subjects that participation in the study will in no way affects their standing at their academic institutions.

Procedures for Monitoring Adverse Events. All study personnel, will be trained regarding how to handle adverse events. Possible adverse events that are unanticipated will be brought to the attention of the PIs, the IRBs, and the NIH project officer. The IRBs who will determine whether it is appropriate to stop the study protocol temporarily or will provide suggestions/modifications to the study procedures as necessary. Possible modifications include adding these possible adverse events to the consent form and re-consenting all study subjects. The PIs will be responsible for monitoring participant safety on a monthly basis at regularly scheduled research meetings. They will keep a written log of all events and ensure that the IRBs are contacted immediately. They will also keep a log of the outcome of IRB decisions regarding adverse events and apprise the research team of any changes that need to occur as a result of IRB decisions.

1. [name] will provide oversight of all recruitment and study procedures and quality assurance checks will be conducted by the Project Director [name] as planned. These quality assurance checks will occur once a week during recruitment and assessment time periods to ensure recruitment goals and validity of the data.
2. All records pertaining to the study and all of the original and electronic files containing collected data will be securely stored by [name] on her password-protected desktop computer and/or a locked file cabinet located in her locked office on GSU campus. Other than [name], only key study personnel will have access to the data files.
3. Specific procedures to ensure the safety of participants will also occur. The proposed research contains some risk for participants; however, the likelihood of adverse events (AEs) is low. During the efficacy trial, we will contact participants via email and texting to not only check in with them but also to promote compliance. All participants who demonstrate they are in need of assistance will be given a 800 telephone number to obtain immediate crisis counseling and a referral 24/7; thus, young women will have access to help in the event they feel distress or are upset.
4. [name] will participate in the monitoring of participants during the course of the research. Should any AEs occur, the project director will be required to immediately contact [name]. [name] will immediately investigate the event and determine the appropriate manner in which to proceed. A report describing the AE will be submitted to the participating Institutional Review Board and to the project officer from NICHD within 10 days of occurrence. In the event a change in procedures is required, an amendment to IRB will occur

promptly, within 10 days.

5. To monitor that our recruitment and retention projections are being met, [name] will hold weekly meetings of the research team to assess recruitment and retention of participants.
6. Drs. [name] and [name] will be responsible for dissemination of study findings through presentation and publication formats. The setting for this research will not be named in publications or presentations.
7. [name], the project director will monitor the data on a weekly basis during assessment periods. She will serve as the project data manager where she will examine the data for accuracy and any inconsistencies. She will rectify any errors and she will maintain a data correction log to record any errors and how they were resolved.
8. [name], a Co-investigator and statistician on the study, will also perform interim analyses to assess the integrity of the data.
9. Finally, [name], will monitor the study using the following criteria:
  - a) Review progress of the surveys as they occur, including analysis of data quality and timeliness; subject recruitment, and other factors that may affect outcome.
  - b) Review serious adverse event reports, provide commentary, and provide oversight to ensure that reports are relayed to individual IRBs and to the Office of Human Research Protections (OHRP), as indicated.
  - c) Review analyses of outcome data of the current study and review reports of related studies to determine whether the current study needs to be changed or terminated.
  - d) Review proposed modifications to the study prior to their implementation.
  - e) Protect the confidentiality of the accumulated data.
  - f) Determine whether and to whom outcome results should be released prior to the reporting of study results.
  - g) Provide appropriate NIH staff with written information concerning their findings relevant to the quality of the data.

